1. SYNOPSIS

Protocol Title: Randomized, Double-blind, Placebo-controlled Dose Escalation Study to Evaluate Safety, Tolerability, Pharmacokinetics, and Pharmacodynamics of Single Doses (intravenous bolus) and constant intravenous infusion over 7 Days of GSK3335065 in Healthy Adult Subjects

Short Title: Safety, Tolerability, Pharmacokinetics, and Pharmacodynamics investigation of GSK3335065 (IV) in healthy adults

Rationale: GSK3335065 is being developed as a treatment for acute pancreatitis with the intent of reducing 3-hydroxykynurenine (3HK) levels to the normal range (or lower) and maintaining them at this level throughout the 7-day treatment period.

Objectives and Endpoints:

Objective	Endpoint
Primary	
 To determine the safety and tolerability of GSK3335065 administered as a single IV bolus (Part A and C), and as a constant IV infusion over 7 days (Part B and C) in healthy volunteers
Secondary	
 Adverse event / Serious Adverse event monitoring Laboratory parameters (hematology, clinical chemistry, urinalysis) 12-lead ECG parameters (PR, QRS, QT, QTcF, etc.) Vital signs (systolic and diastolic blood pressure, heart rate) 
 To determine the pharmacokinetic characteristics of GSK3335065 administered as a single IV bolus (Part A and C), and as a constant IV infusion over 7 days (Part B and C) in healthy volunteers Determine dose/exposure effects of GSK3335065 on KMO inhibition (pharmacodynamics) in healthy volunteers (All Parts) 
 Pharmacokinetic Parameters: $AUC_{(0-t)}$, $AUC_{(0-\infty)}$, t_{last}, C_{max}, C_{avg}, t_{max}, CL, V, $t_{1/2}$ Evaluate changes in levels of TRP metabolites (3HK and KYN)

Overall Design: This is a phase I, first time in human (FTIH), three part, randomized, placebo-controlled dose escalation study that will utilize an adaptive design for combining Single Ascending Dose (SAD) by IV bolus (Part A) with Ascending Doses by intravenous (IV) continuous infusion dosing for 7 days (Part B) in healthy males. Part C will recruit women of non-child bearing potential (WONCBP) only, and a single dose by

IV bolus will be investigated prior to multiple dose (7 day) being investigated. The decision to proceed to the next dose level in Part A will be based on safety and tolerability data obtained up to 8 days post dose from at least 6 subjects at the prior dose level.

Number of Participants: 112 evaluable subjects. Part A will comprise of 64 healthy male subjects (Cohorts 1 to 8). Part B of 32 healthy male subjects (Cohorts 9 to 12). Part C will comprise of 16 women of non child bearing potential (Cohorts 13 to 14).

Treatment Groups and Duration:

Part A will last up to approximately 7 weeks from screening to follow-up. Part A was initiated using an interlocking four period crossover design with two cohorts and the intention that all participants will receive four ascending IV bolus doses of GSK3335065. Subjects in cohorts 1 and 2 received a single dose of 0.1 mg and 0.25 mg GSK3335065, respectively. All subjects from cohorts 1 and 2 will be discontinued from the study.

For operational feasibility, the design of Part A will be changed to a parallel cohort design and dosing will be continued at the third dose level (1.3 mg) (Amendment 3). For each subsequent dose level, a cohort of 8 subjects will receive a single dose of GSK3335065.

Prior to initiation of Parts B and C, a review of all available safety, tolerability, PK and PD data from Part A will be conducted and potential changes to the dosing paradigm, safety observation period and assessments will be communicated in a future amendment to the protocol as appropriate.

Part B will last up to approximately 13 weeks from screening to follow-up. Participants will receive one IV bolus dose of GSK3335065 immediately followed by an IV infusion over seven days.

Part C cohort 7 will last approximately 7 weeks and Part C cohort 8 up to 13 weeks from screening to follow-up. Cohort 7 will comprise of a single IV bolus. Cohort 8 will mirror Part B.

2. SCHEDULE OF ACTIVITIES (SOA)

- The timing and number of planned study assessments, including safety, pharmacokinetic, pharmacodynamic/biomarker or other assessments may be altered during the course of the study based on newly available data (e.g., to obtain data closer to the time of peak plasma concentrations) to ensure appropriate monitoring.
- Any changes in the timing or addition of time points for any planned study assessments must be documented and approved by the relevant study team member and then archived in the sponsor and site study files, but will not constitute a protocol amendment. The Institutional Review Boards (IRB)/Independent Ethics Committees (IEC) will be informed of any safety issues that require alteration of the safety monitoring scheme or amendment of the Informed Consent Form (ICF).

2.1. Part A & C – Cohort 1, 2, 3, 4, 5, 6, 7, 8 & 13, single bolus dose, healthy volunteer subjects

Procedure	Screening (within 28 days of Day 1)	Study Period (Days)									Follow-up (7-14 days following discharge)	Notes
		-1	1	2	3	4	5	6	7	8		
Outpatient Visit	X										X	
Admission to Clinical Unit		X										
Inpatient Stay at Clinical Unit			←-----									
Discharge from Clinical Unit										X		Following completion of all assessments
Informed consent	X											
Inclusion and exclusion criteria	X	X										
Demography	X											
Full physical exam incl height and weight	X											
Brief Physical		X								X	X	Brief physical upon discharge from every cohort (Day 8)
Medical history (includes substance usage)	X											Substances: Drugs, Alcohol, tobacco and caffeine
Clinical Safety Laboratory Assessments (HIV, Hep B and Hep C Screen at screening only ¹)		X	X	X			X		X		X	Screening and day -1 safety labs must be in fasted state. ¹ If test otherwise performed within 3 months prior to first dose of study treatment, testing at screening is not required.
LFTs (ALT, AST, AP, direct and indirect Bilirubin)	X	X	X		X			X		X	X	

Procedure	Screening (within 28 days of Day 1)	Study Period (Days)									Follow-up (7-14 days following discharge)	Notes
		-1	1	2	3	4	5	6	7	8		
cTnI & BNP	X	X	X ²	X		X				X		² 6hrs post-dose
FSH	X											Females only, if required
Urine Drug/Alcohol Breath Test	X	X									X ³	³ Alcohol breath test only
12-lead ECG	X	X	X	X	X	X	X		X	X	X	Triuplicate ECGs will be obtained at screening and predose. Single measurements at 30min, 6hr, 12hr, 24hr, 72hr, 120hr, 168hr post-dose. ECG times may be adjusted once initial PK data is available.

Procedure	Screening (within 28 days of Day 1)	Study Period (Days)									Follow-up (7-14 days following discharge)	Notes
		-1	1	2	3	4	5	6	7	8		
Continuous ECG monitoring			X									Continuous monitoring from -1 hour pre-dose to 24hours post dose. Based on preclinical data levels of parent compound and tryptophan metabolites are expected to reach peak levels within a few hours of the start of dosing. A review of telemetry data will therefore be performed after 24 hours for clinically relevant alerts (see Appendix 9 for guidance). In the absence of such a signal, monitoring will revert to regular ECG assessments. In case clinically relevant changes are observed telemetry will be continued as long as deemed appropriate by the investigator. At the investigator's discretion and in consultation with the medical monitor telemetry could be reinitiated at any time during the study should any potential signals in regular ECG assessments emerge.
Transthoracic Echocardiogram	X											Additional echocardiograms may be performed if increases in cTNI or BNP are observed (see Section 8 for details), or at any time at the discretion of the investigator

Procedure	Screening (within 28 days of Day 1)	Study Period (Days)									Follow-up (7-14 days following discharge)	Notes
		-1	1	2	3	4	5	6	7	8		
Vital Signs	X		X	X	X	X	X				X	VS assessments will be performed in triplicate at screening and at pre-dose. All post dose assessments will be performed as single measurements at 30 min and 1 hr, 6hr, 24hr, 48hr, 72hr, 96hr, 120hr, 144hr, 168hr post-dose as outlined in Section 9.4.2. VS times may be adjusted based on emerging PK data.
Study Treatment			X									
Assessment of infusion site			←-----	-----→								Up to day 8
Blood (PK)			←-----	For sampling time points, see Section 9.5.1-----→						X		Additional blood PK samples may be collected other than those timepoints specified in Section 9.5.1 or on additional days based on emerging data
Urine (metabolism)		X	X									Equivalent to admission on day -1 to pre-dose day 1 and 0-24 hours post-dose as outlined in Section 9.5.2. Part A Cohorts Only.
Blood (PD)			←-----	For sampling time points, see Section 9.7-----→						X		Additional 3HK and PD Biomarker samples may be collected other than those timepoints specified in Section 9.7 or on additional days based on emerging data

Procedure	Screening (within 28 days of Day 1)	Study Period (Days)								Follow-up (7-14 days following discharge)	Notes
		-1	1	2	3	4	5	6	7	8	
PGx Sample				X							Pre-dose if possible. Informed consent for optional genetics research must be obtained before collecting a sample
AE/SAE review			←	=====						→	X
Concomitant medication review	X	←	=====						→	X	

2.2. Part B & C – Cohorts 9, 10, 11, 12 & cohort 14, single bolus dose plus 7 day infusion, healthy volunteer subjects

Procedure	Screening (within 28 days of Day 0)	Study Period (Days)															Follow-up (Day 32 ± 2 days)	LFT Follow-up (Day 62 ± 2 days)	Notes
		-1	1	2	3	4	5	6	7	8	9	10	11	12	13	14	15		
Outpatient Visit	X																X	X	
Admission to Clinical Unit		X																	
Inpatient Stay at Clinical Unit		←	=====												→				
Discharge from Clinical Unit																	X		Following completion of all assessments
Informed consent	X																		
Inclusion and exclusion criteria	X	X																	

Procedure	Screening (within 28 days of Day 0)	Study Period (Days)															Follow- up (Day 32 ± 2 days)	LFT Follow- up (Day 62 ± 2 days)	Notes
		-1	1	2	3	4	5	6	7	8	9	10	11	12	13	14	15		
Demography	X																		
Full physical exam incl height and weight	X																		
Brief Physical		X															X	X	
Medical history (includes substance usage)	X																		Substances: Drugs, Alcohol, tobacco and caffeine
Clinical Safety Laboratory Assessments (HIV, Hep B and Hep C Screen at screening only ²)	X	X	X	X	X	X	X	X	X	X	X	X	X	X	X	X	X		Screening and day -1 safety labs must be in fasted state. ² If test otherwise performed within 3 months prior to first dose of study treatment, testing at screening is not required
LFTs (ALT, AST, AP, direct and indirect Bilirubin)	X	X	X	X	X	X	X	X	X	X	X	X	X	X	X	X	X		
cTnI / BNP	X	X	X	X		X			X		X		X		X		X		6hrs, 24hrs and 72hrs post dose. D7 immediately after end of infusion. D10, D13 and D15 anytime.
Urine Drug/Alcohol Breath Test	X	X															X ³	X ³	³ Alcohol Breath test only
FSH	X																		Females only, if required

Procedure	Screening (within 28 days of Day 0)	Study Period (Days)															Follow- up (Day 32 ± 2 days)	LFT Follow- up (Day 62 ± 2 days)	Notes
		-1	1	2	3	4	5	6	7	8	9	10	11	12	13	14	15		
12-lead ECG	X	X	X	X	X	X	X	X	X	X	X	X	X	X	X	X	X		Triplicate ECGs will be obtained at screening and predose. Single measurements 30min and 6hr, 12hr, 24hr, and on Days 3-15 post-dose (equivalent to 36hr, 48hr, 72hr, 96hr, 120hr, 144hr, 168hr, 192hr, 216hr, 240hr, 264hr, 288hr, 312hr, 336hr, 360hr post-dose). ECG times may be adjusted once initial PK data is available.

Procedure	Screening (within 28 days of Day 0)	Study Period (Days)															Follow- up (Day 32 ± 2 days)	LFT Follow- up (Day 62 ±2 days)	Notes
		-1	1	2	3	4	5	6	7	8	9	10	11	12	13	14	15		
Continuous ECG Monitoring				X															Continuous monitoring from -1 hour pre-dose to 24hours post dose. Based on preclinical data levels of parent compound and tryptophan metabolites are expected to reach peak levels within a few hours of the start of dosing. A review of telemetry data will therefore be performed after 24 hours for clinically relevant alerts (see Appendix 9 for guidance). In the absence of such a signal, monitoring will revert to regular ECG assessments. In case clinically relevant changes are observed telemetry will be continued as long as deemed appropriate by the investigator. At the investigator's discretion and in consultation with the medical monitor telemetry could be reinitiated at any time during the study should any potential signals in regular ECG assessments emerge.
Transthoracic Echocardiogram	X																		Additional echocardiograms may be performed if increases in cTN or BNP are observed (see Section 8 for details), or at any time at the discretion of the investigator

Procedure	Screening (within 28 days of Day 0)	Study Period (Days)															Follow-up (Day 32 ± 2 days)	LFT Follow-up (Day 62 ± 2 days)	Notes
		-1	1	2	3	4	5	6	7	8	9	10	11	12	13	14	15		
Vital Signs	X	X	X	X	X	X	X	X	X	X	X	X	X	X	X	X	X		VS assessments will be performed in triplicate at screening and pre-dose. Single measurement at 30 min and 1 hr, 6hr, 24hr, and on Days 3-15 post-dose as outlined in Section 9.4.2. VS times may be adjusted based on initial PK data.
Columbia Suicide Severity Rating Scale (C-SSRS)	X	X			X			X									X		
Cognitive Assessments (6-CIT, fingertapping test and NPI)		X				X			X										
Study Treatment			←-----→																
Assessment of infusion site			←-----→																Up to 36 hrs post-start of infusion
Blood (PK)			←-----For sampling time points, Section 9.5.1-----→															Additional blood PK samples may be collected other than those timepoints specified in Section 9.5.1 or on additional days based on emerging data	
Urine (metabolite)		X			X														Equivalent to admission on day -1 to pre-dose day 1 and 48-72 hours post-dose. PART B Cohorts Only.

Procedure	Screening (within 28 days of Day 0)	Study Period (Days)															Follow- up (Day 32 ± 2 days)	LFT Follow- up (Day 62 ± 2 days)	Notes
		-1	1	2	3	4	5	6	7	8	9	10	11	12	13	14	15		
Blood (PD)			←-----For sampling time points, Section 9.7-----→															Additional 3HK and PD Biomarker samples may be collected other than those timepoints specified in Section 9.7 or on additional days based on emerging data	
Bile Sampling (enterotest)						X												Only to be performed at highest dose administered. Part B only	
PGx Sample			X															Pre-dose if possible. Informed consent for optional genetics research must be obtained before collecting a sample	
AE/SAE/PSRAE review			←-----→													X			
Concomitant medication review	X		←-----→													X			

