Treatment Period	For Cohorts 1 and 2, each subject will take part in four dosing session. During each study period subjects will be in-house from the day prior to dosing until Day 4 post dose when they will be discharged after post dose assessments have been completed. Subjects in Cohorts 1 and 2 will return to the unit approximately 3 weeks later to be dosed again on the following day. Following the completion of period 4, subjects will return as out-patients for any post-dose assessments.
Washout Period	Approximately 10 to 21 days between doses ^a .
Follow-up	7-14 days after final study drug administration in the Cohort. If warranted, additional follow-up visits may be scheduled.
Total Duration	Approximately 19 weeks

Table 5 Study Duration of Cohorts 3, 4, 5, 6, 7, 8 (Part A)

Screening	All screening assessments to be completed within 28 days prior to the first dose.
Treatment Period	Each subject will take part in one dosing session. During each study period subjects will be in-house from the day prior to dosing until Day 8 post dose when they will be discharged after post dose assessments have been completed. All subjects may return to the unit approximately 2 weeks after discharge from the unit as out-patients for any post-dose assessments.
Follow-up	Approximately 7-14 days after discharge from the unit. If warranted, additional follow-up visits may be scheduled.
Total Duration	Approximately 7 weeks

5.1.2. Part B: Multiple Ascending Dose (IV Bolus followed by an IV Infusion over 7 days) in Males

Prior to initiation of Part B, a review of all available safety, tolerability, PK and PD data from Part A will be conducted and potential changes to the dosing paradigm, safety observation period and assessments will be communicated in a future amendment to the protocol as appropriate.

Part B is a randomized, placebo-controlled, sequential panel, multiple ascending dose (IV bolus followed by continuous IV infusion over 7 days), double-blind (Sponsor unblinded) trial to evaluate the safety, tolerability, pharmacokinetics and pharmacodynamics of GSK3335065 in healthy male subjects. Subjects will be assigned to one of four Cohorts (9, 10, 11 or 12), and subjects will only participate in one single cohort. In each cohort subjects will be randomized to receive an IV bolus on day 1 subsequently followed by a continuous IV infusion for seven days. of either the active study drug (n=6) or placebo (n=2).

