Sentinel Dosing: We will stagger each new ascending dose in Part B so that 2 leading subjects will be dosed first. One of these subjects will be randomized to receive active treatment, and the second will receive placebo. Once these subjects have completed the 7-day dosing period, the safety and tolerability data will be reviewed. If there are no clinically relevant safety or tolerability concerns, the remaining 6 subjects will be dosed.

During the course of the 7 day infusion period the participants will be given two approximately 30 minute windows on Day 3 and Day 6 after completion of PK and PD collection in order to perform activities (i.e. shower) without having the canula inserted. The window may be modified based on emerging safety and PK data.

Table 6 Study Duration of Cohorts 9, 10, 11, 12 (Part B)

Screening	All screening assessments to be completed within 28 days prior to the first dose.
Treatment Period	During each study period subjects will be in-house from the day prior to dosing until Day 15 when they will be discharged after post-dose assessments have been completed. Subjects will return to the unit as out-patients for any post-dose assessments.
Follow-up	Approximately 14 days after discharge following termination of study drug administration. If warranted, additional follow-up visits may be scheduled. Additional Liver Function Tests (51 days after discharge)
Total Duration	Each cohort is approximately 13 weeks

5.1.3. Part C: IV Bolus followed by an IV Infusion over 7 days in WONCBP

Prior to initiation of Part C, a review of all available safety, tolerability, PK and PD data from Part A will be conducted and potential changes to the dosing paradigm, safety observation period and assessments will be communicated in a future amendment to the protocol as appropriate.

Part C will be a randomized, placebo-controlled and double-blind trial to evaluate the safety, tolerability, pharmacokinetics and pharmacodynamics of GSK3335065 conducted in WONCBP only, and will consist of two cohorts (13 and 14). Cohort 13 will investigate a single intravenous dose, and Cohort 14 will investigate a multiple dose (continuous IV infusion over 7 days). In each cohort subjects will be randomized to receive repeat doses of either active (n=6) or placebo (n=2). Cohort 13 and 14 can commence upon safety, tolerability and PK data from the equivalent dose group is available from the male cohort. Cohort 13 will complete prior to cohort 14 initiation.

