In cohort 14 participants will be given two 30 minute windows on Day 3 and Day 6 after completion of PK and PD collection in order to perform activities (i.e. shower) without having the canula inserted. These windows may be modified based on emerging safety and PK data.

Table 7 Study Duration of Cohort 13 (Part C)

Screening	All screening assessments to be completed within 28 days prior to the first dose.
Treatment Period	Each subject will take part in a single dosing session. Subjects will be in-house from the day prior to dosing until Day 8 post dose when they will be discharged after post dose assessments have been completed. Subjects will return as out-patients for any post-dose assessments.
Follow-up	Approximately 7-14 days after discharge from the unit. If warranted, additional follow-up visits may be scheduled.
Total Duration	Approximately 7 weeks

Table 8 Study Duration of Cohort 14 (Part C)

Screening	All screening assessments to be completed within 28 days prior to the first dose.
Treatment Period	During the study period subjects will be in-house from the day prior to dosing until Day 11 when they will be discharged after post-dose assessments have been completed. Subjects will return to the unit as out-patients for any post-dose assessments.
Follow-up	14 days after discharge following termination of study drug administration. If warranted, additional follow-up visits may be scheduled. Additional Liver Function Tests- 51 days after discharge
Total Duration	Approximately 13 weeks

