5.4.3. Maximum dose/exposure in Part B

The highest dose planned to be explored will target a concentration just over 100 times the Ki in PART B. Modelling suggests that the highest anticipated dose (73.4 mg total dose on day 1 followed by 50.4 mg/day on days 2-7) should achieve reductions of 3HK in excess of 90% even if the increase in KYN observed is substantially larger than that seen in the rat (20 fold compared to 6-10 fold). This value remains below (177-fold for Cmax and 75-fold for AUC(0-24h)) the plasma concentration at the NOAEL in the toxicity studies in rats and dogs. The highest dose also remains below the threshold for increased drug induced liver injury (DILI) risk (100 mg). Higher doses may be administered if exposures are lower than predicted but the maximum exposure will not exceed the 75-fold exposure margin in terms of AUC to the NOAEL.

This dose is anticipated to reduce 3HK levels by >90%. Preclinical data support that lowering 3HK levels through KMO inhibition >90% in humans is anticipated to be safe as KMO deficient mice have undetectable levels of 3HK and elevation of metabolites, such as kynureneine (KYN), kynurenic acid (KYNA) and anthranilic acid (AA), but appear viable and healthy. A robust decrease in 3HK of >90% was observed in the dog 7-day dose range finding study. 3HK levels could not be determined in the rat study. However the mid dose used in this rat study had previously been shown to reduce 3HK levels by ~85% on the first day of dosing in a pharmacology study. Any adverse effects of changes in 3HK would have been noted in these studies.

Table 10 Part B planned doses, predicted exposures, and anticipated margins to rat NOAEL. 4 ascending doses are planned in Part B.

	Dose range IVB & IV infusion	Expected (%) KMO inhibition	Targeted Concentration (Cmax) (ug/ml)	Margin to NOAEL (Cmax)	AUC(0-168h) (ug.hr.mL ⁻¹)	Margin to NOAEL (AUC 0-24h)
Anticipated starting dose	IVB 0.14 mg + IV Inf. 0.012 mg/h	25%	0.005 (0.6xKi)	31800	0.9	13067
Anticipated pharmacologically active dose	IVB 7.5 mg + IV Inf. 0.63 mg/h	>60%	0.27 (30xKi)	589	47	250
Anticipated pharmacologically active dose	IVB 12 mg + IV Inf. 1.1 mg/h	>85%	0.45 (50xKi)	353	85	138
Highest anticipated dose	IVB 23 mg + IV Inf. 2.1 mg/h	>90%	0.9 (100xKi)	177	156	75

5.4.4. Part C:

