9.4.8. Assessment at infusion site

The infusion site will be assessed at various times up to 36 hours post-dose using a 0–3 scale as follows: Grade 0=none; Grade 1=pain or itching or erythema; Grade 2=pain or swelling, with inflammation or phlebitis; Grade 3=ulceration or necrosis.

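### In the 7-day infusion cohorts the scheduled infusion-site grade stops at 36 h of 168 h, and for the single-bolus cohorts the protocol gives two different end points for it

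*Protocol*

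**What the plan says.** For Cohorts 9-12 and 14, the infusion-site row of Protocol Schedule of Activities 2.2 carries the note "Up to 36 hrs post-start of infusion". Protocol 9.4.8 states, without separating cohorts: "The infusion site will be assessed at various times up to 36 hours post-dose using a 0–3 scale as follows". The risk table in 3.3.1 gives the same limit as part of the mitigation for local reactions to intravenous dosing.

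Protocol 5.1.2 describes the Part B treatment as an IV bolus followed by "continuous IV infusion for seven days". It also allows "two approximately 30 minute windows on Day 3 and Day 6 after completion of PK and PD collection" during which the cannula is out. Section 5.1.3 repeats this for the women's infusion cohort: "In cohort 14 participants will be given two 30 minute windows on Day 3 and Day 6".

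For the single-bolus cohorts (Part A and Cohort 13), the note in Schedule of Activities 2.1 runs the same assessment to Day 8.

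Protocol section 4 makes safety and tolerability of the 7-day infusion part of the primary objective. The endpoints listed for it are adverse events, laboratory values, ECG and vital signs; the site grade is not among them. The SAP reports the site assessments in one listing (Listing 35) and has no summary table for them.

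**The concern.** The protocol names local reactions as a study risk and adopts a 0-3 grade to watch for them. In the cohorts with prolonged infusion, that scheduled check ends on the second day of seven. A reaction that builds with cannula dwell time or cumulative infusion would appear after the grading has stopped. The cannula also comes out and the infusion resumes twice, and no grade is planned on either occasion. Had Part B run as written, a low set of site grades would have described the first day and a half, not the regimen whose tolerability was in question.

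A separate problem concerns Part A, which was dosed. With two end points in force, a reader of Listing 35 cannot tell whether an absent grade after 36 h is missing or was never planned.

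**Working it through.** **Inputs.** Grading limit: 36 h from start of infusion (Schedule 2.2). Infusion length: seven days (5.1.2). Top dose level: 23 mg bolus plus 2.1 mg/h (Table 10), stated as "73.4 mg total dose on day 1 followed by 50.4 mg/day on days 2-7" (5.4.3). Sampling before each cannula-free window: about 08:00 (9.5.1). Cohort size: 6 active and 2 placebo (10.2.1).

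**1. Infusion length.** 7 × 24 = 168 h, which agrees with the AUC(0-168h) column of Table 10. The daily doses confirm round-the-clock infusion: 50.4 / 2.1 = 24.0 h per day, and 23 + 2.1 × 24 = 73.4 mg on Day 1.

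**2. Coverage.** 36 / 168 = 21.4% graded; 168 − 36 = 132 h, or 132 / 168 = 78.6%, with no scheduled grade.

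**3. Planned subjects.** Cohorts 9-12 and 14 make 5 × 8 = 40, of whom 5 × 6 = 30 receive active drug and 5 × 2 = 10 placebo.

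**4. Cannula-free windows.** The documents give no clock time for dosing, so a range is assumed. Each window follows the 08:00 sample. For a start at clock hour *c*, that sample falls at 48 + 8 − *c* hours on Day 3 and 120 + 8 − *c* hours on Day 6.

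| Start of dosing (assumed) | Day 3, 08:00 | Day 6, 08:00 |
|---|---|---|
| 06:00 | 50 h | 122 h |
| 08:00 | 48 h | 120 h |
| 12:00 | 44 h | 116 h |
| 18:00 | 38 h | 110 h |
| 20:00 | 36 h | 108 h |

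For any start from 06:00 to 18:00 both windows come after grading ends. The Day 3 sample reaches the 36 h limit only with a start at 20:00 or later. The Day 6 window is outside it throughout.

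**5. Other scheduled looks at the site.** The brief physical examination covers lungs, cardiovascular system and abdomen as its minimum (9.4.1), and as Schedule 2.2 reads it is not placed during the infusion. The minimum data set for Part B escalation (5.4.2, Appendix 3) lists adverse events but not site grades.

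**6. Single-bolus cohorts side by side.** Schedule 2.1: to Day 8. Sections 3.3.1 and 9.4.8: to 36 h, all cohorts. Day 8 corresponds to 168 h, so the two limits differ by 168 − 36 = 132 h. Table 4 ends the in-house stay of Cohorts 1 and 2 on Day 4, so a Day 8 limit could not have been met in the unit for them. The conflict matters most for Cohort 3.

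**The case against.** **Adverse events.** The strongest reply is that local reactions after 36 h are not lost. Adverse events are collected from admission to follow-up (9.2.1), each is rated mild, moderate or severe (Appendix 4), and subjects live in the unit throughout the infusion. A reader might infer from the 36 h limit that local tolerability of the infusion was largely unmeasured. The documents do not support that, because adverse events are the named primary endpoint and the site grade is not an endpoint. What remains is narrower. Detection would rest mainly on open-ended questions (9.2.2), which can miss redness that the subject does not mention. The intensity scale is also not the 0-3 scale, so findings before and after 36 h are not comparable.

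**Non-clinical data.** Section 3.3.1 treats local reactions as a general concern with intravenous drugs and reports no local irritation in 14-day infusion studies in two species. A 36 h limit stated in three places may be deliberate. That lowers the expected yield of longer grading. It does not explain the choice of 36 h for a seven-day infusion.

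**Provisional plan.** Part B and C assessments were to be reviewed after Part A and could be amended (5.1), and section 2 lets assessment timing change without an amendment. This stands, but no such change is written.

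**Other inferences that go too far.** One is that the design favours the bolus with a longer window: that rests on a single note in Schedule 2.1, which 3.3.1 and 9.4.8 contradict. Another is that a new cannula site would go ungraded: the protocol does not say whether the cannula is re-sited.

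**Wording of 9.4.8.** Its 36 h is counted from dose, which for an infusion could be read as from the end. The Schedule 2.2 note settles this as from the start.

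**Conclusion.** The point holds as a gap in the planned measurement. In Cohorts 9-12 and 14 no scheduled site grade covers 132 of 168 h (79%) of the infusion, its end, or the two cannula-free windows. The statement about the windows assumes dosing starts before about 20:00. The coverage figure relies on the written note, since the span of the arrow in that row cannot be read from the text version of the table.

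A reader might infer that reported results are affected. For the infusion they are not: the SAP records that the study stopped after sentinel dosing in Part A Cohort 3 and that Parts B and C no longer apply, so the 40 subjects are planned numbers only. The conflict between Day 8 and 36 h does bear on reported data, through the reading of Listing 35, and the passages must be reconciled.

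**What to change.** In Schedule of Activities 2.2, 3.3.1 and 9.4.8, extend the existing 0-3 grade for the infusion cohorts to at least once daily through the end of infusion and until discharge. Add a grade when the infusion resumes after each cannula-free window, and record which site was graded. State that hours are counted from the start of infusion.

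Reconcile Day 8 with 36 h for the single-bolus cohorts, and state the window that applied in a footnote to Listing 35. Before setting the last grading day, reconcile the Cohort 14 discharge day, which is Day 15 in Schedule 2.2 and Day 11 in Table 8.

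The cost is text edits and a brief daily bedside inspection of subjects who are already in-house with daily vital signs. For Cohort 14 that holds only up to whichever discharge day is confirmed; both candidate days fall after the infusion ends. No dose or stopping rule changes.
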